3.4 Removal of Subjects from the Study

Subjects may be withdrawn from the study by the Investigator or Sponsor for any of the following reasons:

- subject did not meet enrollment criteria (inclusion/exclusion criteria);
- subject has an AE that warrants study discontinuation;
- subject lost to follow-up during the study or voluntary withdrawals;
- significant protocol deviation (e.g., study product noncompliance);
- withdrawal at the Investigator's discretion.

If possible, any subject who is withdrawn from the study will have the reason for withdrawal documented in the subject's source documents and/or appropriate CRF and, at the time of withdrawal, all exit procedures performed (i.e., procedures for Visit 6). All subjects who do not complete the study will be required to return all un-used study products provided by the Sponsor.

3.5 Concomitant Therapy

For excluded medications prior to study start and during the study, see the inclusion/exclusion criteria (Sections 3.2.1 and 3.2.2). Subjects will be instructed to contact the study staff to report any changes in product usage during the study.

At each visit, new concomitant medications or changes to current concomitant medications will be documented.

Subjects will be instructed to only use the test products and pads and/or pantiliners which have been supplied for all of their feminine protection needs during their participation in the study. Subjects will be instructed to use their normal care practices except refrain from using douching

substances, feminine hygiene products, or applying powders, perfumes, wipes, or emollients to the genital area for at least 24 hours prior to the start of tampon use and during the study. After completion of the study, the subjects may resume using douching substances, powders, perfumes, wipes, or emollients per their normal habits and practices

3.6 Treatments

3.6.1 Method of Assigning Subjects to Treatment Groups

Subjects will be assigned a 4-digit subject number (e.g., 1001, 1002, etc) at Visit 1 (screening). At Visit 2, eligible subjects will be randomly assigned a randomization number using a balanced computer-generated randomization supplied by the Sponsor to the site. A unique randomization number (e.g., 101, 102, 103, etc) will be assigned for each study product assigned to subjects.

3.6.2 Treatments Administered

At Visits 2-5, each subject who fulfilled all the entry criteria will receive one of 4 treatments along with a daily and monthly questionnaire for use until their menstruation is complete. Subject instructions will be given to each subject (Appendix 10).

All study products will be provided by the Sponsor in a double-blind manner.

The study product label for the treatment phase will contain the Study Number and a space where the Subject Number will be recorded by the study site prior to dispensing. The label will also contain the randomization number and a statement clearly identifying an investigational product and other information as dictated by internal regulatory requirements.

3.6.3 Identity of Study Products

During the initiation visit, the monitor will review procedures for the management of study product. Throughout the study, additional shipments of study treatments and supplies may be sent to the study center to assure a continuous supply to all study subjects.

Details regarding the study products are as follows:

Test Product(s) – Regular Absorbency (6 to 9 grams)	
Tampax	91069721
100% cotton fiber tampon –	91500859
Tampax	92321409
Tampax	94522993

Back-up Pads/Liners
Always Ultrathin
Always Pantiliners
Always Overnight

3.6.4 Management of Study Products

The Investigator will have overall responsibility for the use of the study product. Under no circumstances will the Investigator allow the study products to be used other than as directed by this protocol. The Investigator or qualified study center designee(s) will provide a signed acknowledgment for receipt of the study products and a signed acknowledgment for return of study product containers and unused study product. An accurate record of the dispensing of all study products must be maintained. Upon completion or termination of the study, remaining study product and administration materials will be returned to the Sponsor, unless otherwise instructed by the Sponsor.

Qualified study center designee(s) must receive study product deliveries, record the receipt, and assure that the study product is handled and stored safely and properly. The invoice must be reconciled against the study product received. Any extra/damaged study product will be destroyed at the study center or sent to the Sponsor for destruction as instructed and documented by the Sponsor.

Copies of all invoices and dispensing records for the study product must be kept at the study center as part of required study documentation. At the end of the study, the study center must be able to reconcile delivery records with records of study product received, dispensed, and returned. Any discrepancies will be documented.

Upon receipt and until dispensed, all study product should be securely stored at controlled room temperature (20°C - 25°C or 68°F-77°F with excursions allowed between 15°C - 30°C or 59°F-86°F). Temperature excursions should be infrequent and last less than 24 hours.

3.6.5 Blinding

This is a double-blind study with limited access to the randomization code. The study product codes will be controlled by the Sponsor. The study treatment sequence each subject will receive will not be disclosed to the Investigator, other study center personnel, or other Sponsor representatives.

Bag packaging will be identical for all study products. All study products will be similar in appearance. The study will be unblinded for analysis only after the database has been locked. Study treatment assignments will be revealed to the Investigator when the final clinical report is issued.

3.6.6 Breaking the Blind

If the blind is broken (e.g. for a subject who has an AE that warrants study discontinuation) it may be broken for only the subject in question. The Sponsor must be notified immediately if the Investigator/designee is unblinded during the course of the study. Pertinent information regarding the unblinding of a subject's treatment code must be documented in the subject's source documents and the eCRF.

3.7 Measurement, Assessment, and Sample Collection

3.7.1 Evaluation Assessments

Data from this study will be collected through multiple assessments. These include:

- Questionnaires (per use and monthly)
- Vaginal assessment (discharge and pH)
- Clinical Vaginal exam (vaginal exam)

3.7.2 Safety Assessments

Subject safety will be assessed with vaginal exams, at screening and at various time points throughout the study.

Safety assessments will also include the collection of AEs reported by the subjects or observed by the investigator or study center personnel. Subjects should be asked whether, since the time of the last observation or visit, they had any of the following:

- experienced any changes in well-being,
- used any new medications or supplements,
- changed medication regimens (both prescription and non-prescription), or
- been hospitalized or had any accidents.

Questions should be of a general nature and should not suggest symptoms.

When an AE is suspected, all relevant evaluations will be carried out and appropriate treatment provided. Additional follow-up will be performed as necessary, recorded in the subject's source documents, with the results provided to the Sponsor. Subjects who experience any clinically significant AE will remain under medical supervision until the Investigator deems the AE to be resolved, stabilized, or no longer serious enough to warrant follow-up. Laboratory values that are abnormal (whether or not they are assessed as AEs) may be followed at the discretion of the Investigator until resolved or stabilized.

For AE definitions and reporting requirements, refer to Section 5.6.

3.7.3 Sample Collections

pH samples for evaluations will be obtained at Visit 1(screening) and Visits 2 thru 6. These will be collected and processed according to instructions (Appendix 7)

Microbiome samples will be collected at Visit 1 (Screening) and Visits 3, 4, 5 and 6. These will be collected and processed according to instruction (Appendix 9). A vaginal microbial swab will be collected for the purpose of assessing the vaginal microbial community of the study population. Analyses will be coordinated by Procter & Gamble's Microbiology Group and is not

considered part of the clinical objectives of this study. Only microbial DNA analysis will be conducted. No human DNA analysis will be performed.

Samples will be collected using only the 4-digit subject # in keeping with Good Clinical Practices.

Samples will be stored in a -70°Celsius freezer at the Procter & Gamble Micro Lab for a maximum of 5 years, after which, all specimens will be destroyed per P&G's policy for specimen destruction.

The results of this testing will not result in a commercially valuable product.

Subjects may withdraw their consent to participate in this testing or to have her samples used for analysis. The Microbiologist will destroy the samples collected from the subject and will delete any data collected from the analysis of the samples. The microbiologist will document this process for the Study File.

Testing does not have any clinical, diagnostic or therapeutic implications for the individual subjects. Therefore, the results will not be reported to the Investigators, the subjects or their primary care physicians. There will not be any follow-up with the subjects regarding this testing”.

4.0 Statistical Methods

4.1 Analysis Population

The Intent-to-treat (ITT) population is defined as all eligible subjects who are enrolled into the study, randomized to treatment, and are given their assigned test products for use. The Per-protocol (PP) population is defined as all subjects in the ITT population who are compliant with the study protocol and complete all four months of the study. Given the duration of the study and likelihood of some panelist drop-out, analyses will be performed on both the ITT and PP populations.

4.2 Determination of Sample Size

As the prior data that is available is years old on the treatments in this study, the sample size of 65 subjects was determined using clinical results based on expert judgment related to relevant publications/past clinical studies.

4.3 Method of Assigning Subjects to Treatment

Subjects will be randomly assigned to one of 4 treatment sequences using an encoded program supplied by the Sponsor.

4.4 Statistical Analysis Plan

No formal hypothesis testing is planned. Product Acceptance will be assessed by medical/clinical with regards to the tolerability of the four treatments based on a body of evidence associated with multiple assessments of vaginal health and adverse events. The primary conclusion will be derived from the clinical assessments including vaginal erythema, ulcerations, abrasions, vaginal pH, vaginal discharge, and AE's.

Prior to statistical analysis, all data will be checked for accuracy, completeness and compliance to protocol. Analyses will be completed using PC SAS Release 9.4.

Demographic data will be summarized in tables of descriptive statistics by treatment sequence to assess overall balance between assigned sequences.

Summary descriptive statistics will be provided for all parameters. Confidence intervals (95% Confidence intervals) will be constructed for all clinical assessments for each treatment code. Any data reported as 'unable to evaluate' will be treated as missing and excluded from the analysis.

The frequencies of vaginal discharge color and consistency responses will be tabulated for each visit/treatment. Depending on the distributions, categories may be collapsed prior to statistical analysis. The frequencies for normal vs. abnormal classifications will be tabulated per visit/treatment. Ninety-five percent CIs around the proportion with abnormal classification, and corresponding odds ratios will be constructed.

The frequencies of erythema scores will be tabulated for each visit/treatment. Also per visit/treatment, 95% CIs will be constructed around: (1) the proportion of subjects with erythema, and (2) the proportion of subjects with moderate or severe erythema. CIs for the corresponding odds ratios also will be constructed.

The frequencies for abrasion and ulceration will be tabulated for each visit/treatment. For each of these parameter, 95% CIs around the proportions and odds ratios will be constructed.

Additional analyses may be conducted to further understand the data.

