- 18) have history of or current diagnosis of AIDS/HIV, organ transplant, neoplasia, liver disease, renal disease, deep vein thrombosis, pulmonary embolism, haemophilia, neutropenia, autoimmune disease, major depression or any other medical condition,

which in the opinion of the Investigator would preclude study participation (*exception...stable dose of Thyroid medication for at least 6 months prior to enrollment*);

- 19) currently using a vaginal probiotic therapy (self-reported);
- 20) have participated in a clinical study with exposure to any investigational drug product within 30 days prior to this study;
- 21) have a vaginal erythema grade of ≥ 2.0 and/or the presence of abrasions and/or ulcerations as determined by investigator, at the screening visit;
- 22) have taken antibiotics or antifungals within last 4 weeks (Topical use of antibiotics or antifungals outside the perineal/genitourinary area is allowed at the discretion of the Investigator);
- 23) have started a new hormonal birth control in the previous 4 months or plan changing hormonal birth control throughout the study period;
- 24) currently experiencing bladder, uterine or rectal prolapse (investigator to verify at screening visit).
- 25) history of led or laser vaginal therapy within last 6 months (self-reported).

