Vaginal Health General Procedures

In General

A physician will conduct all vaginal exams on all subjects at the time points indicated in the Study Events table of the protocol.

At the Screening visit, Vaginal swabs will be collected to rule out positive results Trichomonas, BV and Yeast, Chlamydia, and Gonorrhea (STI).

Supplies:

- Plastic, clear speculums should be used
- Sterile saline
- Appropriate lighting such as a gooseneck lamp or a headlamp; same lighting should be used at all examination intervals
- Aptima Swabs

Vaginal Assessments, Documentation of Findings, and Follow Up PRN

The study Physician of record will conduct the procedures and vaginal exam/assessments appearing below. Any potential confounding activities will also be assessed during the vaginal exam i.e., sexual activity within the past 48 hours or intra-vaginal product use other than study supplied tampons.

All findings either normal and abnormal, will be documented in the eCRF Form, noting score (for erythema) and absence or presence of abrasion, ulceration, laceration, and color and character of vaginal discharge and any evidence of sexually transmitted disease. Document the location, extent, and detailed description of any findings in comments.

Study subjects who have abnormalities or irritation noted on their gynecological examination form may be scheduled for a follow up examination. The Study Physician will determine whether follow-up is necessary. Follow up examinations will occur 1-2 weeks before the start of the subject's next menstrual period.

Procedure Order:

- Subjects will be placed in the dorsal lithotomy position.
- Observe external genitalia and record any findings on eCRF Form;
- A speculum will be inserted into the vagina to visualize the upper 1/3 of the vagina;
- Using the scales and descriptors outlined in the protocol and Appendices, record all findings on eCRF Form;

Appendix 5

ERYTHEMA GRADING SCALE

- 0** No apparent cutaneous involvement.
- 0.5** Greater than 0, less than 1.
- 1** Faint but definite erythema, no eruptions or broken skin or no erythema but definite dryness; may have epidermal fissuring.
- 1.5** Greater than 1, less than 2.
- 2** Moderate erythema, may have a few papules or deep fissures, moderate-to-severe erythema in the cracks.
- 2.5** Greater than 2, less than 3.
- 3** Severe erythema (beet redness), may have generalized papules or moderate-to-severe erythema with slight edema.
- 3.5** Greater than 3, less than 4.

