- 4** Generalized vesicles or eschar formations or moderate-to-severe erythema and/or edema.

NOTE: The degree of reaction expressed by such descriptive terms as "moderate" and "severe" is, in itself, subjective. Such terminology can be accurately understood only through experience.

Any reaction of greater severity than Grade 4 should be described in detail. Unusual reactions not described by the scale should also be described.

TYPICAL EXAMPLES OF HALF-GRADE SCORES

- 0.5 Faint, barely perceptible erythema or slight dryness (glazed appearance).
- 1.5 Well-defined erythema or faint erythema with definite dryness, may have epidermal fissuring.
- 2.5 Moderate erythema with barely perceptible edema or severe erythema, may have a few papules or moderate-to-severe erythema.
- 3.5 Moderate-to-severe erythema with moderate edema or moderate-to-severe erythema with isolated eschar formations or vesicles.

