Appendix 6**Vaginal Examination (sample)**

Ulceration/Abrasion These lesions will be noted as either No (absent) or Yes (present) only.

	Erythema¹		Abrasion²		Ulceration³	
	Yes	No	Yes	No	Yes	No
Labia Minora:						
Introitus:						
Lower Vaginal Walls:						
Middle Vaginal Walls:						
Upper Vagina (incl. Fornices):						
Cervix:						

Prolapse Present: Bladder Yes No Uterine Yes No Rectal Yes No

Based on this Examination:

Is a follow-up visit indicated?

Yes* No

*If yes, state reason: _____

Does the subject meet (continue to meet) study eligibility?

Yes No*

*If no, state reason: _____

¹ Erythema Scale. Record scores as: 0.0, 0.5, 1.0, 1.5, etc.

² Abrasion – ‘yes’ indicates partially disrupted epithelium, blood vessels may be intact or disrupted. Diffuse area of demarcation.

³ Ulceration – ‘yes’ indicates tear in or sloughing of epithelium, blood vessels may be intact or disrupted. Sharp demarcation.

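### Erythema is graded in half-steps at six sites, but section 4.4 compares products only by odds ratios on two cuts; a within-woman difference in grade should be added alongside

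*Combined protocol and SAP*

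**What the plan says.** **Grading.** Appendix 5 runs from 0 ("No apparent cutaneous involvement") to 4 ("Generalized vesicles or eschar formations or moderate-to-severe erythema and/or edema"), with half-grades between. The form in Appendix 6 has rows for six sites: labia minora, introitus, lower, middle and upper vagina, and cervix. Its boxes are yes/no, but the footnote on erythema says "Record scores as: 0.0, 0.5, 1.0, 1.5, etc".

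**Analysis.** Section 4.4 tabulates the scores by visit and treatment. It then plans that "95% CIs will be constructed around: (1) the proportion of subjects with erythema, and (2) the proportion of subjects with moderate or severe erythema" and adds that "CIs for the corresponding odds ratios also will be constructed". The same section promises descriptive statistics for every parameter and a 95% CI for each clinical assessment by product. It rules out formal testing, leaves product acceptance to medical judgement across several assessments (erythema is named first), and allows unspecified further analyses.

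**Thresholds.** Section 4.4 puts no numbers on the two cuts. Exclusion criterion 21 (section 3.2.2) bars women who "have a vaginal erythema grade of ≥ 2.0 and/or the presence of abrasions and/or ulcerations as determined by investigator, at the screening visit". Section 3.3 names the same grade among findings that may lead to an extra examination.

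**The concern.** The physician records a graded sign, but the only measures that set one product against another reduce it to two yes/no questions. Criterion 21 means that every woman is at 0 to 1.5 at screening. Within that range Appendix 5 separates barely perceptible redness (0.5) from grade 1.5, "Well-defined erythema or faint erythema with definite dryness, may have epidermal fissuring". On the natural reading of the cuts, a product that moves women from the first to the second leaves both odds ratios where they were.

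What is at stake is how much the erythema comparison tells those who judge acceptance. Two odds ratios near 1 could sit beside a real shift in grade, with no estimate of that shift between products and no interval for it. Each woman uses all four products, so the data for a within-woman estimate will already exist.

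**Working it through.** The plan's one design figure, 65 completers, cannot be reproduced: section 4.2 rests it on expert judgement and gives no rate, SD or power. It is used below only as n.

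**1. Moves that the cuts cannot see.** Levels: 4/0.5 + 1 = 9. Possible worsenings: 9 x 8/2 = 36. Appendix 5 gives 0 as no involvement, 0.5 as the first grade with visible redness, and 2 as the first whole grade labelled moderate. The natural cuts are therefore >0 and >=2.0, and the bands are 0, 0.5-1.5 and 2.0-4.0. Moves that stay inside a band: 3 x 2/2 = 3 in the middle and 5 x 4/2 = 10 at the top, so 13 of 36. With cuts at >=1.0 and >=2.0 the count is 1 + 1 + 10 = 12. With the upper cut at >=1.5 it is 1 + 15 = 16, whether the lower cut is >0 or >=1.0.

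**2. Worked example (assumed distribution).** Grades 0, 0.5, 1, 1.5 and 2 held by 25, 25, 10, 3 and 2 of 65 women. A second product moves k women from 0.5 to 1.5 and changes nobody else.

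- Any erythema: 40/65 on both products, OR = (40/25)/(40/25) = 1.00.
- Moderate or severe: 2/65 on both, OR = (2/63)/(2/63) = 1.00.
- Mean paired difference: k/65. SE = sqrt[k(65-k)/(65 x 64)]/sqrt(65).
- k = 7: 0.11 (95% CI 0.03 to 0.19). k = 13: 0.20 (0.10 to 0.30). k = 20: 0.31 (0.19 to 0.42).

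These intervals are narrow because no other grade varies. A rerun let 40% of exams vary at random by half a grade and moved each woman at 0.5 to 1.5 with probability 0.25 or 0.5. The full grade excluded no difference in 27% and 68% of runs, the any cut in about 3%, and the upper cut in almost none.

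**3. General shift (assumed rates).** The plan gives no erythema rates, so a range is shown. Inputs: 65 women, one grade per exam, two products, second product shifted up 0.4 SD on a latent normal scale (mean shift 0.14-0.25 grade), 4,000 replicates. Grade 2 or more in the reference product was 1, 3, 5 and 8% in the four rows. The cuts were tested by mid-p McNemar and the full grade by paired t; a signed-rank test agreed within 2 points. Each cell is the chance of excluding no difference, at within-woman correlation 0.3 / 0.6.

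| Any erythema, reference product | Any cut | Moderate-or-severe cut | Full grade | Gain over better cut (points) |
|---|---|---|---|---|
| 20% | 44% / 54% | 1-2% | 47% / 63% | 3 / 9 |
| 40% | 49% / 63% | 14% / 13% | 62% / 82% | 13 / 19 |
| 60% | 46% / 59% | 23% / 23% | 69% / 87% | 23 / 28 |
| 80% | 34% / 41% | 27% / 34% | 71% / 90% | 37 / 49 |

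A repeat with a different assumed spread of grades gave gains of 3-6 points at 20%, 10-16 at 40%, 22-28 at 60% and 35-45 at 80%. At 10% any erythema the gain was 0-4 points.

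**4. Two special patterns.**

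- Shift confined to 0.5-1.5 (mean +0.2 grade, both cut proportions unchanged): cuts 2-5%, full grade 58% / 74%.
- Onset only (any erythema 40% to 58%, all new cases at 0.5): any cut 61% / 73%, full grade 20% / 28%.

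**The case against.** The strongest reply is that nobody would be blind to such a shift. Section 4.4 tabulates every score and promises descriptive statistics and a 95% CI for each product, so a drift from 0.5 to 1.5 could appear in the tables and in the product means. The plan tests nothing, and its aim is to confirm tolerability of four products, not to rank them, so power is not its decision rule. The upper cut is not arbitrary either: >=2.0 is the protocol's own threshold at screening and for possible re-examination.

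All of this stands, and it lowers the weight of the point. A reader might infer that graded worsening would go unseen, or that the cuts have no basis. The documents support neither. What remains is that the summaries are per product. No difference between products on the grade is specified, nor an interval for one, nor any use of the pairing.

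It can also be said that section 4.4 gives no numeric cuts. If having erythema meant >=1.0, the 0.5-to-1.5 move would be seen: in the worked example, k = 7 gives (22/43)/(15/50) = 1.71. That is correct, but 12 of 36 worsenings would still be missed, and the ambiguity is itself a reason to write the numbers down.

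Finally, the pattern that both cuts miss entirely needs a product that deepens existing redness and creates none. Under a general shift the any cut still detects 34-63%.

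**Conclusion.** The point holds as a cheap improvement. On the natural reading of the cuts, the only specified between-product measures for erythema cannot register worsening within 0.5-1.5 or within 2.0-4.0, and the summaries that could show it carry no product difference. Adding the full grade gains about 3-9 points at 20% any erythema and 13-49 points at 40-80%. Below 20% the gain is close to nil.

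These sizes rest on assumed rates, a 0.4 SD latent shift, 65 women, a paired analysis of each cut (the plan does not say how its odds ratios are formed) and one grade per exam, although six sites are recorded. The count of 13 of 36 rests only on the scale and the two cuts.

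A reader might go further and infer that the full-scale difference should lead the erythema comparison. The figures do not support that: when harm is only new 0.5 grades, the any cut is clearly better (61% / 73% against 20% / 28%). Each measure sees harm that the other misses, so they belong side by side.

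**What to change.** In section 4.4:

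- Define the two cuts as >0 and >=2.0, and keep their proportions and odds ratios.
- Define one erythema grade per exam as the worst of the six sites, with by-site results as support.
- Add alongside, not as the lead: the within-woman product difference in that grade with a 95% CI, from a mixed model with product, period and a random woman effect.
- Add a cumulative-logit mixed model as sensitivity analysis.

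The cost is a few lines of text and two SAS models on data already collected, written in before unblinding. There are three drawbacks. There is one more summary to read. The mean difference treats half-grades as equally spaced, which the cumulative-logit model checks. Grades 0.5 to 1.5 can also reflect dryness, so a difference in that range is not redness alone.

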2.0 Study Objectives

2.1 Objective(s)

1. The objective of this study is to support a claim of “clinically tested” while women wear tampon(s) during their full menstrual period with medical and gynaecological assessments of vaginal health and consumer self-reported assessments of comfort.
2. To confirm the tolerability of four (4) tampon products based on a body of evidence associated with multiple assessments of vaginal health and adverse events. The primary conclusion will be derived from the clinical assessments including vaginal erythema, ulcerations, abrasions, vaginal pH, vaginal discharge, and Adverse Events (AEs).
3. Usage diaries and questionnaires are added for learning purposes regards to comfort and tolerability.

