3.0 Investigational Plan

3.1 Study Design

This will be a 4-consecutive menstrual cycle, single center, randomized, controlled, double-blind, crossover study conducted with approximately 100 menstruating women to complete with 65. Women aged **18-55** who report having consistent menstrual cycles and who typically use tampons as their main source of feminine protection during their menstrual cycles. Each subject will test each of the four (4) tampon products, testing one (1) product per monthly menstrual cycle over the course of this study. The order of the products tested will be randomized for each subject. Subjects will be given a tampon use diary to be completed after the use of each tampon and a Monthly Comfort Questionnaire to be completed at the end of each menstrual cycle.

Subjects will be instructed to call after the start of each period and schedule their gynecological examination visit **within 72** hours after the use of their last tampon for each period. Women who choose to use a backup menstrual protection product in addition to their assigned test tampon, will be provided currently marketed Always Ultrathin, Always Pantiliners and Always Overnight pads in the product’s marketed packaging. Subjects will be given instructions, including to refrain from using any douche products, sexual lubricant (except lubricated condoms), vaginal medications, suppositories, feminine deodorant spray, powder (in the perineal area), or vaginal wipes at least 48 hours prior to the screening visit and for the duration of their study

participation. Subjects will be given instructions to refrain from sexual activity for at least 48 hours prior to every gynecological examination visit. Subjects will be asked to refrain from bathing and use of antibacterial soaps while on the study, and from any vaginal hair removal 12 hours prior to the screening visit. During the tampon use phase of the study, subjects will be queried for changes in their health and medications at every visit. If during their monthly gynecological examination, a vaginal or pelvic organ associated adverse event is reported or found, if the subject wishes to continue in the study, the PI will make the continuance decision on a case by case basis after consultation with the Sponsor.

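### Do the odds ratios in Section 4.4 need a stated reference, a paired method and a zero-event rule?

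*Combined protocol and SAP*

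**What the plan says.** Section 3.1 describes a "single center, randomized, controlled, double-blind, crossover study conducted with approximately 100 menstruating women to complete with 65", in which "Each subject will test each of the four (4) tampon products, testing one (1) product per monthly menstrual cycle". Each completing woman therefore contributes four post-cycle examinations.

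Section 4.4 plans frequencies and 95% confidence intervals for the proportions, by visit or treatment, with odds ratios added:

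- Discharge: "Ninety-five percent CIs around the proportion with abnormal classification, and corresponding odds ratios will be constructed".
- Any erythema, and moderate or severe erythema: "CIs for the corresponding odds ratios also will be constructed".
- Abrasion and ulceration: "For each of these parameter, 95% CIs around the proportions and odds ratios will be constructed".

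The same section states that "No formal hypothesis testing is planned" and leaves product acceptance to medical and clinical assessment. This matches the second objective in Section 2.1: "To confirm the tolerability of four (4) tampon products based on a body of evidence".

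No reference product, repeated-measures method or zero-event rule is given for the odds ratios. Section 3.6.3 lists all four products under one test-product heading. That list has gaps where descriptors may have been removed, so the lack of a visible control label there is not evidence either way.

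**The concern.** An odds ratio needs two groups, and Section 4.4 does not name them. Four products give three odds ratios against one reference, six if all pairs are shown, or four if each product is set against screening. The same women supply all the groups, so an interval that treats them as separate samples has the wrong width. A matched-pair conditional odds ratio is another quantity again. If abrasion or ulceration is rare, some products will have no events and the odds ratio cannot be computed.

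These outcomes feed the primary conclusion. Under Section 3.6.5 the study is unblinded for analysis once the database is locked, so choices not written down earlier would be made with product results in view. At stake is whether the comparative part of the tables could read differently depending on who programs it.

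**Working it through.** The documents give no event rates or within-woman correlations. Apart from the 65 completers, the counts, rates and correlations below are assumptions. The plan has no odds ratio or precision figure of its own to reproduce.

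**1. What each odds ratio compares.** If screening were the reference, exclusion criterion 21 (Section 3.2.2) would matter. It bars women with abrasions, ulcerations or an erythema grade of 2.0 or more at screening. Appendix 5 labels grade 2 as moderate, so three of the five outcomes have zero screening events by design, and their odds ratios would be infinite or undefined. That points an analyst to comparisons between products.

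The choice of reference product hides nothing, because every pairwise odds ratio follows from the tabulated counts. With 13, 15, 18 and 23 events in 65 women, the odds are 13/52 = 0.250, 15/50 = 0.300, 18/47 = 0.383 and 23/42 = 0.548. The last product has

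- 0.548/0.250 = 2.19 against the first,
- 0.548/0.300 = 1.83 against the second,
- 0.548/0.383 = 1.43 against the third.

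**2. Pairing.** Take 13/65 and 23/65 with 9 women positive on both.

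- Odds ratio: (23 × 52)/(42 × 13) = 2.19; its log is 0.784.
- Unpaired variance: 1/13 + 1/52 + 1/23 + 1/42 = 0.1634, standard error 0.404, interval exp(0.784 ± 1.96 × 0.404) = 0.99 to 4.84.
- Paired marginal variance: subtract 2(n11/n − p1p2)/(n p1q1p2q2) = 2(0.1385 − 0.0708)/(65 × 0.1600 × 0.2286) = 0.0569. This leaves 0.1065, standard error 0.326, interval 1.16 to 4.15.
- Conditional odds ratio: the discordant counts are 23 − 9 = 14 and 13 − 9 = 4, so 14/4 = 3.50, with interval exp(1.253 ± 1.96 × √(1/14 + 1/4)) = 1.15 to 10.6.

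Section 4.4 ties the odds ratios to the tabulated proportions. That makes 2.19, the marginal value, the natural reading; 3.50 cannot be read off those proportions.

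More generally, at equal rates the unpaired interval on the log scale is too wide by a factor 1/√(1 − φ), where φ is the correlation between the two yes/no results:

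| Event rate | latent ρ 0.3 | ρ 0.5 | ρ 0.7 |
|---|---|---|---|
| 2% | 1.034 | 1.086 | 1.195 |
| 5% | 1.053 | 1.121 | 1.250 |
| 10% | 1.072 | 1.154 | 1.300 |
| 20% | 1.093 | 1.191 | 1.355 |
| 30% | 1.105 | 1.211 | 1.385 |

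Under positive correlation the error is toward caution. In simulation (65 women, rates 10% to 35%, ρ 0.3 to 0.7) unpaired intervals covered about 97% to 99.5% of the time and paired ones about 94% to 96%.

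**3. Zero events.** The chance that a given product has none is (1 − p)^65: 27% at a 2% rate, 3.6% at 5% and 0.1% at 10%. Treating products as independent, at least one of four has none with probability 1 − (1 − (1 − p)^65)^4: 71%, 14% and 0.4%. Allowing for within-woman correlation gives 62% to 69%, 12% to 13% and under 1%.

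The planned summary still works in that case. For 0/65 the two-sided exact upper limit is 1 − 0.025^(1/65) = 5.5%. Pairing does not rescue the odds ratio at these rates. For 2% against 5% with ρ 0.7, only about 71% of simulated datasets gave one, and the paired interval then covered about 93%.

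**4. What does not depend on any of this.** Each woman enters a product's proportion once, so the per-product interval has no repeated-measures problem. In the example these are 13/65 = 20.0% (± 1.96√(0.1600/65) = 9.7 points) and 23/65 = 35.4% (± 1.96√(0.2286/65) = 11.6 points), whatever is done with the odds ratio.

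**The case for a change.** The best case for a change is that two programmers could follow Section 4.4 faithfully and print different tables. In the example one interval includes 1 and the other does not. A conditional analysis would also move the estimate, from 2.19 to 3.50. If the odds ratios compare products, they are the only between-product measure the section names, and the introduction says that the design is meant to detect differences between products. Section 4.4 refers to no fuller plan, and a few sentences would settle the matter at almost no cost.

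All three omissions stand, as does the point that marginal and conditional odds ratios are not interchangeable. What does not follow is that a conclusion is at risk. The value 1 has no role in any decision here, since no test or limit is attached to it. The introduction's remark reports past experience and is not a criterion. The plan is silent on method and does not prescribe an unpaired analysis, so there is nothing wrong to correct. The after-unblinding argument has force where a choice can turn a result. Here the counts behind every odds ratio are tabulated, and a reader can recompute the marginal estimate for any pair.

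**Conclusion.** The plan leaves detail out of a descriptive summary, and analysts can fill it sensibly: compare products with one another, give the odds ratio that matches the tabulated proportions, allow for the same woman using all four products, and mark an odds ratio as not estimable when a product has no events. If the pairing were ignored, the intervals would be about 3% to 38% too wide, with the same point estimate. If the odds ratio could not be computed, the count and the exact interval for the proportion would remain.

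These sizes rest on 65 completers, assumed rates of 2% to 30% and assumed latent correlations of 0.3 to 0.7; with no correlation the excess width is nil. The judgment that no change is needed rests on two facts in Section 4.4: no formal hypothesis is tested, and acceptance is a medical judgment on several kinds of evidence. If a test, margin or product ranking were attached to the odds ratios, the reference and method would need to be fixed in advance.
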